Low grade gliomas are the most common pediatric central nervous system malignancies and can occur in different parts of the brain. Patients who undergo gross total resection, usually those with hemispheric tumors, have an excellent prognosis with surgical resection alone. Patients for whom gross total resection is not achievable have a significant risk of disease progression. Therefore, these patients benefit from adjuvant therapy. Multiple chemotherapy regimens have shown some efficacy in residual tumor, but more than 50% of patients experience recurrences. Radiation has been shown to be an effective therapy in the treatment of these tumors. Because of concerns regarding radiation toxicity especially in young children, and progression despite chemotherapy, novel approaches are needed. This protocol represents an attempt to measure the efficacy and safety of use of pegylated interferon for patients with recurrent, refractory Juvenile Pilocytic Astrocytomas (JPA) or optic pathway gliomas. It provides a different approach to the commonly used treatment modalities. Patients with progressive, refractory or symptomatic JPA who have received radiation and who have received at least one prior course of chemotherapy will be eligible for this study. All patients on the study will receive a course of pegylated interferon 1 mcg/kg/dose weekly lasting for up to 2 years. Response will be evaluated with MRI every 12 weeks. The objectives of this study are to determine the response of children with chemotherapy-refractory progressive JPA or optic pathway gliomas (OPG) to weekly pegylated interferon alpha-2b. The secondary objectives include to better identify the toxicities of weekly pegylated interferon alpha-2b in pediatric patients with unresectable, refractory, recurrent JPAs or optic pathway gliomas, to evaluate various magnetic resonance imaging techniques for noninvasive monitoring of metabolic and biologic changes in the tumors and to evaluate the quality of life for patients with recurrent, refractory JPAs who receive therapy with pegylated interferon alpha-2b. The primary end point is to determine the response rate. The secondary end point is to determine the Event Free survival. A two-stage design has been selected to evaluate the response rate. If the treatment demonstrates at least a 25% response rate, we would consider it a promising regimen for further study. A response rate less than 5% is considered evidence of unpromising regimen. Seventeen evaluable pediatric patients with JPA or OPG will be accrued. If at least 3 responders are seen among the 17 patients, this will be considered evidence of a promising response rate for further evaluation.

EXPERIMENTAL DESIGN SCHEMA:

Cycle# 1	Day0	Day7	Day 14	Day 21	Day28	
PEG-Interferon (1 mcg/kg/week)	X	X	X	X	X	
MRI imaging						EVERY 12 WEEKS.

EXPERIMENTAL DESIGN SCHEMA:

Note: Each cycle is 28 days

PD = Progressive Disease

SD = Stable Disease

PR = Partial Response

CR = Complete Response

1.0 OBJECTIVES

1.1 PRIMARY STUDY OBJECTIVES

To determine the objective response of children with recurrent or Refractory and radiographically or clinically progressive Juvenile Pilocytic Astrocytomas and Optic Pathway Gliomas who are treated with pegylated interferon alpha-2b Response will be determined as complete response or partial response.

1.2 SECONDARY STUDY OBJECTIVES

1.2.1

To estimate event free survival (EFS) (based on standard two or three-dimensional tumor measurements) for children with recurrent, refractory or progressive Juvenile Pilocytic Astrocytomas and Optic Pathway Gliomas who are treated with Peginterferon.

1.2.2

To define the toxicities of long term weekly pegylated interferon alpha-2b in pediatric patients with refractory, recurrent and progressive Juvenile Pilocytic Astrocytomas and Optic Pathway Gliomas.

1.2.3

To compare response categories and EFS across the 3 MR sequences (T2-weighted, FLAIR, T1-weighted post-contrast).

1.2.4

To evaluate the quality of life for patients with recurrent, refractory and progressive Juvenile Pilocytic Astrocytomas and Optic Pathway Gliomas who receive therapy with pegylated interferon alpha-2b

2.0 BACKGROUND

2.1 Introduction/Rationale for Development

Low-grade gliomas (LGGs) represent the most common pediatric central nervous system (CNS) malignancy, accounting for more than half of all such tumors. The most common locations are the cerebellum, followed by the cerebral hemispheres and by the deep midline structures such as the hypothalamus, thalamus, lateral and 3rd ventricles, and the corpus callosum. These tumors are also found along the visual pathways and in the brainstem and in the spinal cord.

Pediatric LGGs include pilocytic, fibrillary, protoplasmic, gemistocytic, giant-cell astrocytomas, or pleomorphic xanthoastrocytoma, oligodendrogliomas and oligoastrocytomas. They belong to the WHO classification as grade I and II. Juvenile Pilocytic Astrocytomas (JPAs) occur predominantly in young children and make up the majority of LGGs found along the optic pathway, as dorsally exophytic brain stem tumors, and in the cerebellum. Grossly, they appear well circumscribed, and in the cerebellum are often cystic, with a mural nodule. They typically, but not always, enhance on MR imaging. JPAs have been particularly associated with neurofibromatosis type 1 (NF-1), in this population lesions are mostly incidental findings and some of them can have indolent courses and close monitoring with imaging studies is recommended.

Patients with JPA patients who have gross total resection, especially those with tumors located in the cerebellar and cerebral hemispheres, have excellent survival at 8 years 99% +/- 0.8% as well as excellent event free survival (EFS). From CCG9891 and POG9130, the results of 518 pediatric patients with low grade gliomas that only underwent surgical resection and no other treatment modality, which had evidence of residual disease, the EFS at 5 years was 56%. Patients younger than 5 years of age had worse EFS than the older counterpart; however this difference does not translate into worse overall survival. [1] JPAs that cannot be completely resected, mostly due to location in or near important structures, are likely to progress and will require additional therapy. Effective treatment modalities include radiation and chemotherapy.

Radiation therapy, while effective, has long term effects that can be minimized if the modality can be delayed or avoided.

Merchant conducted a phase II study that included 78 pediatric patients with unresectable low grade gliomas who received radiation therapy. The 5 year EFS was 87% +/- 4.4 and 10 year EFS was 74.3% +/- 15.4%. The mean and standard error cumulative incidence of vasculopathy was 4.79% +/- 2.73 at 6 years and it was higher for patients younger than 5 years of age at the time of radiation. The main reason to the delay in radiation in young patients with LGG is to reduce their risk of vasculopathy [2]. Additionally, patients with LGG after radiation treatment experienced some adverse endocrine events that were limited. The 3 more common hormone replacements were: growth hormone, thyroid and glucocorticoid. The 5- and 10-year confident intervals for growth hormone replacement were 46.0% +/- 7.2% and 48.9% +/- 7.4%. The thyroid hormone replacement, 61.4% +/- 7.5% and 64.0% +/- 7.5%. The glucocorticoid replacement was 19.2% +/- 5.8% and 19.2% +/- 5.8%. Additionally, in the CBCL activities scores, for patients with neurofibromatosis -1 who underwent treatment with radiation have a decrease in the score from 44.2 to 36.8 after 5 years of treatment, while the average score of a patient without NF-1 remained unchanged at 44.2806 despite radiation therapy. [2]

2.2 Chemotherapy for pediatric low grade gliomas:

COG 9952 was the first randomized upfront clinical trial for low grade gliomas. It investigated two chemotherapy regimens for children less than 10 years with unresected LGGs. Regimen A included carboplatin and vincristine (CV). Regimen B included thioguanine, procarbazine, lomustine and vincristine (TPCV). Only regimen A included patients with neurofibromatosis-1. Of 274 randomly assigned between both regimens, 137 received regimen A and 137 received regimen B. The 5-year EFS and overall survival (OS) rates were 45% ± 3.2% and 86% ± 2.2%, respectively. The 5-year EFS rates were 39% ± 4% for CV and 52% ± 5% for TPCV (P = 0.10). Independent factors by multivariate analysis that were predictive of worse EFS and OS are younger age and tumor size greater than 3 cm. Additionally, the location of the tumor in the thalamic region was also associated with poor survival. [3]

Boufet et al conducted a phase II trial with vinblastine for recurrent or refractory pediatric low grade glioma dose of 6mg/m²/dose. 36% of patients had complete, partial or minor response. 23/51 patients have not had progression. 5 year OS was 93.2% +/- 3/8% and 5 year PFS was 42.3% +/- 7.2%. Vinblastine as a weekly regimen was comparable to first line COG 9952. [4]

The experience of bevacizumab for low grade gliomas is limited to case series. Ten children heavily treated for multiply recurrent LGG received the combination of bevacizumab and irinotecan for a median of 5.2 years of age, range 1.5-11.1 years. 70% patients had an objective radiographic response (1 CR, 3 PR and 3 minor Responses). Other clinical improvements were: improved visual acuity, improved

motor function, weight gain in patients with a diencephalic syndrome, and reversal of psychomotor retardation. Dose-limiting toxicities included transient leukoencephalopathy and grade 3 proteinuria. The majority of patients had durable responses. Six patients remained on treatment for almost 2 years. Multiply recurrent low-grade gliomas in children demonstrated responses to the combination of bevacizumab and irinotecan.[5, 6]

A second series reported 7 children who received bevacizumab with irinotecan. Tumor reduction could be observed in 6/7 (85%) patients with recurrent low-grade gliomas. Bevacizumab-related acute toxicity appears to be low in children, even in combination with irinotecan. [7]

Finally, 14 pediatric patients with multiply recurrent low-grade gliomas were treated with bevacizumab and irinotecan for at least twelve months of follow-up after completion of initial therapy. Median treatment duration was 12 months (range, 1 - 24 months). 12/14 patients had an objective response; two had stable disease, and no progressions. 13/14 patients progressed after stopping bevacizumab at a median of four months. Four patients were retreated with bevacizumab alone and all responded or stabilized on treatment. Bevacizumab-based therapy is successful at inducing LGG regression and stabilization after initial therapy or with repeated treatment, although nearly all patients' tumors will progress off-therapy. Toxicities are not insignificant but usually reversible (6). A subsequent report, gave additional details of responses after progression of LGG when retreated with bevacizumab in 4/4 patients, however alternative dose strategies such as bevacizumab as a single agent and interval does every 3 weeks were evaluated. [8]

Therashima et al evaluated pediatric patients with centrally located LGG who received either chemo or radiation to better understanding the risk factors along with the effects of interventions on long-term outcome through a retrospective chart review. Forty-seven patients with a median follow-up of 79 months were included in the analysis. The 5-year EFS and OS were 53% and 96%. The 5-year PFS for those that received radiation upfront was 76% vs. those who received chemotherapy as a first line 37%. $p=0.02$. The 5-year PFS after salvage RT was 55% for those who progressed after chemotherapy. [9]

Pilocytic astrocytomas often have a solid and cystic component at presentation or recurrence. The management of the cystic component of the tumor can be difficult when gross total resection is not possible. Multiple treatment options are available, including additional resection, fenestration of the cyst, and placement of an Ommaya reservoir for intermittent aspiration, systemic chemotherapy, and radiation therapy. In a retrospective analysis, the cases of children with pathology confirmed WHO grade 1 astrocytomas and identified patients with complications arising from the cystic portion of the tumor were reported. 54 patients with tumors with a cystic component. In 31.4% there was progression of the cystic portion of the tumor. The optic pathway/hypothalamus was the most common location for progressive tumor cysts. Surgical resection was attempted in all cases at least once; a total of 39 surgical procedures were performed. Cyst fenestration was attempted in 35.2%. Ommaya reservoir was placed in 47%. 9 patients got external beam radiation and 5/9 (56%) had stabilization of cyst growth with no additional therapies. Intra-cystic administration of P32 was given to only one patient. Chemotherapy was used in 65% of cases. 7 of the 11 children who received chemotherapy required more than one regimen. This retrospective study shows that management of tumor-associated cysts in low grade gliomas remains challenging. (Wolf D, Cohen KJ, Neuro-oncology vol 14, 2012, issue suppl i69-i81, abstract LG-35)

2.3 Interferon Alpha

Mechanism of Action: The interferons (IFN) are a family of glycoproteins with antiproliferative, antiviral, and immune-modulating capabilities. Studies have shown that they are involved in control of cell function and replication, but their mechanisms of action are not fully known. They bind to cell surface receptors, resulting in a signal transduction that induces or suppresses gene expression.

The interferons induce protein synthesis, inhibit mitotic activity, modify cell membranes and regulate immune effector cells. They block cell transition from G0/G1 into the S phase of the cell cycle. They are known to suppress the expression of the c-myc and c-fos proto-oncogenes, and receptors for certain growth factors. Other effects of peg interferon alpha-2b include inhibition of viral replication in virus-infected cells, the suppression of cell cycle progression/cell proliferation, induction of apoptosis, anti-angiogenic activities, and numerous immunomodulating activities, such as enhancement of the phagocytic activity of macrophages, activation of NK cells, stimulation of cytotoxic T-lymphocytes, and the upregulation of the Th1 T-helper cell subset.

Peginterferon raises concentrations of effector proteins such as serum neopterin and 2'5' oligoadenylate synthetase, raises body temperature, and causes reversible decrease in leukocyte and platelet counts.

The type I interferons (IFN-alpha and IFN-beta) are also negative regulators of cell growth and can modify cell differentiation. Interferon-alpha can be induced by foreign cells, tumor cells, and virus-infected cells that stimulate B- lymphocytes, null lymphocytes and macrophages.

Numerous clinical trials have been performed investigating the utility of interferons for viral diseases and cancer. The interferons have been approved by the FDA for several clinical indications, including hairy cell leukemia, chronic myelogenous leukemia and melanoma.

Interferon therapy has been associated with a variety of side effects including an acute flu-like syndrome with malaise, fever and chills, irritability, fatigue and musculoskeletal pain. Longer-term effects include depression, anorexia, headache and cognitive impairment. At least some of these effects are felt to be dose-related.

Clinical studies using alpha, beta and gamma interferons have been performed on patients with malignant brain tumors using different methods of administration, including intravenous, subcutaneous, intramuscular, intrathecal and intracavitary. The results have been mixed.

2.4 Peg-interferon:

There are 2 brand names of peginterferon alpha 2b on the market, both from the same manufacture.

-PEG-Intron™(SCHERING-PLOUGH/MERCK) PEG-Intron™ is a covalent conjugate of recombinant interferon alfa-2b with monomethoxy polyethylene glycol (PEG), that was FDA-approved in January, 2001 for use in patients with Hepatitis C. **-Sylatron (SCHERING-PLOUGH/MERCK)** is a covalent conjugate of recombinant alfa-2b interferon with monomethoxy polyethylene glycol (PEG). The average molecular weight of the PEG portion of the molecule is 12,000 daltons. The average molecular weight of the SYLATRON molecule is approximately 31,000 daltons. The specific activity of pegylated interferon alfa-2b is approximately 0.7×10^8 international units/mg protein. Initial approval for the adjuvant treatment of melanoma.

Interferon alfa-2b is a water-soluble protein produced by recombinant DNA techniques from the bacterial fermentation of an E. Coli strain with a genetically engineered plasmid containing an interferon gene from human leukocytes. (package insert)

Pegylation increases the biologic half-life of the compound, enabling it to be administered once weekly, and also reduces the peaks and troughs in blood levels. Pegylated interferon uses a 12 kilodalton PEG that is attached to interferon in a linear fashion. Maximal serum concentrations occur between 15-44 hours after dosing, and are sustained for up to 72 hours. The mean elimination half-life is 22-60 hours in patients with Hepatitis C virus infection. Renal elimination accounts for 30% of the clearance. Although there is extensive data on the use of Pegylated interferon in adults with hepatitis C and melanoma, there is limited data on its use in children or in patients with other cancers.

2.5 Clinical Data of Interferon in Cancer

2.5.1 Interferon and Gliomas: In gliomas, Nagai et al reported a partial response in 2 / 9 patients with glioblastoma treated with rIFN-alpha A, and 40% response rate (1 complete response, 7 partial responses) in 20 patients with glioblastoma treated with human fibroblast interferon-beta. [10]

Two phase II trials of temozolomide with interferon alpha-2b (pegylated and non-pegylated) in patients with recurrent glioblastoma multiforme demonstrated PFS at 6 months was 31% for 29 evaluable patients in the IFN study and 38% for 26 evaluable patients in the PEG group. In recurrent GBM patients, in combination with both studies of standard dose TMZ with either IFN or PEG showed improved efficacy when compared to reports using TMZ alone. The grade 3 or 4 toxicities more common were leucopenia and thrombocytopenia. Grade 3 or 4 fatigue occurred in 18% of patients on both studies. Lymphopenia was not seen frequently. [11]

In a pediatric study involving children with recurrent malignant tumors treated with recombinant interferon- β , 2 of 9 children with brainstem gliomas had a partial response (>50% reduction in tumor size) and 2 children had prolonged disease stabilization (1 child for 3.5 years).[12]

In a follow-up study of pediatric patients with brainstem gliomas treated with IV recombinant β -interferon during hyperfractionated radiation therapy, 13 of 32 patients required dose modifications due to hepatic or hematologic toxicity. [13]

The optimal dosing for interferon alpha has not yet been established, although it has been used to treat a variety of neoplasms. It has traditionally been administered in high doses = 3,000,000 U/m², 2-3x/week. Significant side effects have limited its use.

In one study in which interferon alpha-2a was administered to pediatric patients with recurrent or progressive craniopharyngiomas at a dose of 8,000,000 U/m² daily for 16 weeks, followed by the same dose 3 times a week for an additional 32 weeks, the need for radiation therapy was significantly delayed in 6 of 15 patients, but more than 50% of the patients experienced significant toxicity requiring intervention or dose reduction within the first 8 weeks of therapy. [14]

2.6 Pegylated interferon in Clinical Studies and Case Series

-Pegylated interferon in Children with Diffuse Intrinsic Pontine Gliomas: Warren et al conducted phase II trial of Pegylated interferon for children with diffuse intrinsic pontine glioma (DIPG). Pegylated interferon was administered as a low-dose of 0.3 µg/kg continuous exposure beginning 2 to 10 weeks after the completion of radiation therapy until they developed disease progression. Thirty-two patients (median age, 5.3 years; range, 1.8-14.8 years) received a median of 7 cycles of therapy. PEGylated interferon was well tolerated. The 2-year survival rate was not significantly improved compared with the historic cohort. The median time to progression was 7.8 months. DIPG compared with an historic control population, it did delay the time to progression. The scientific reason for the low dose of interferon was the anti-angiogenic affect seen in animal models. [15]

-Pegylated interferon in Children with Cystic Craniopharyngiomas:

-Pegylated interferon in Children with Progressive Neurofibromas: The safety and tolerability of pegylated interferon was evaluated in a phase I trial in patients unresectable progressive or symptomatic plexiform neurofibromas (PN).Thirty patients (median age 9.3 years) were treated. All 5 patients at the 4.5 µg/kg DL came off study or required dose reductions for behavioral toxicity or fatigue. During the first 4 weeks, no dose-limiting toxicity (DLT) was seen in patients treated at the 3 µg/kg dose level (DL), however similar DLT on the 3 µg/kg DL became apparent over time. At the 1.0 µg/kg DL, there was 1 DLT (myoclonus) in 12 patients enrolled. 11/16 patients had pain improvement and 13/14 patients had a decrease in size of a palpable mass. Volumetric analysis had a 15%-22% decrease in volume in 5/ 17 patients (29%). The dose recommended for phase II of pegylated interferon for pediatric patients is 1 µg/kg/wk. This trial is currently ongoing.[17] (www.clinicaltrials.gov)

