5.0 DOSE MODIFICATIONS FOR TOXICITY

For patients who are unable to tolerate the protocol-specified dosing schedule, dose adjustments are permitted in order to keep the patient on study drug. If administration of Pegylated interferon must be interrupted because of unacceptable toxicity, drug dosing will be interrupted or modified according to rules described below. Toxicity will be assessed using the NIH-NCI Common Terminology Criteria for Adverse Events, version 5.0

https://ctep.cancer.gov/protocoldevelopment/electronic_applications/docs/CTCAE_v5_Quick_Reference_5x7.pdf

Pegylated interferon dose level modification guidelines

Patients who experience significant toxicity as listed in section 5.0 will have the dose reduced by 25% of the dose on subsequent cycles. Two dose reductions are allowed, as long as there is no evidence of progressive disease (see section 10.4) Patients who again experience dose modifying toxicity after 2 dose reductions will be taken off protocol therapy.

Dose Modification for Toxicity	Dose and schedule
Standard dose	1mcg/kg/dose
Dose Modifications	First Dose Modification: reduction by 25% of dose
	Second Dose Modification: reduction by 50% of dose
	Permanently discontinue if unable to tolerate second dose modification

*For patients whose weight is greater than 150kg, the maximum dose of Pegylated interferon to be administered is 150mcg/dose/week. (See table above)

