9.0 STATISTICAL CONSIDERATIONS

9.1 Sample Size and Study Duration

This study will enroll patients without NF-1 and patients with NF-1. Based on the established accrual goals and incidence of pediatric low grade gliomas 17 patients can be accrued within 36 months of protocol activation, given an average of 1 patient per 2.1 months. Assuming 15% of patients are not evaluable or eligible, 20 patients total will be required to be enrolled on this study.

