9.6 Monitoring for Toxicity

“Toxic events” will be defined as one in which a patient has two dose reductions and then experiences another significant toxicity as defined in Section 5.0, irrespective of attribution. A two-stage stopping rule will be used to monitor for an excessive number of these toxic events. All patients described below must be evaluable for toxicity. All patients who receive at least one dose of Pegylated interferon will be evaluable for toxicity. A review of treatment feasibility and patient safety will be undertaken if we observe at least 2/9 or 4/17 toxic events. The rule will be met about 4% of the time if the true incidence of toxic event is 10%, and 90% of the time if the true incidence is 30%.

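### Section 9.6 does not say when toxic events are counted, and its 90% detection is approached (88%) only if the counts stay open until every child's toxicity status is complete

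*Combined protocol and SAP*

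**What the plan says.** Section 9.6 describes the rule this way: "A two-stage stopping rule will be used to monitor for an excessive number of these toxic events". The boundaries and the consequence are: "A review of treatment feasibility and patient safety will be undertaken if we observe at least 2/9 or 4/17 toxic events". The section puts the chance of meeting the rule at about 4% if the true incidence is 10%, and at 90% if it is 30%.

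Two definitions in the same section determine what is counted. The numerator is a child for whom "a patient has two dose reductions and then experiences another significant toxicity as defined in Section 5.0". The denominator is wide: "All patients who receive at least one dose of Pegylated interferon will be evaluable for toxicity".

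Section 5.0 says a child with significant toxicity "will have the dose reduced by 25% of the dose on subsequent cycles". Section 4.3 sets 28-day cycles and up to 26 of them. Section 9.1 plans 17 patients within 36 months, "given an average of 1 patient per 2.1 months".

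On the timing of toxicity the plan offers one report, from the phase I trial in plexiform neurofibromas summarised in section 2.6: "During the first 4 weeks, no dose-limiting toxicity (DLT) was seen in patients treated at the" 3 µg/kg level, where it emerged later.

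Section 9.6 gives no minimum exposure, no date for either count, and no statement on whether the 2/9 count stays open while the first nine are followed further.

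**The concern.** The stated probabilities are of binomial type. They treat each of the 9 or 17 children as having a final answer: toxic event or none. A child who has had one dose has no final answer, because three successive qualifying toxicities cannot yet have happened. That child nevertheless enters the denominator as event-free.

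If the counts are read early, events that would occur later are missing from the numerator, and the rule detects less than the plan states. This matters because 9.6 holds the only numerical boundary for non-fatal toxicity in a treatment lasting up to two years. Section 9.7 covers toxic deaths only, and section 9.8 is estimation without a threshold.

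**Working it through.** **Inputs from the documents.** Boundaries 2/9 and 4/17, incidences 10% and 30%, and the definitions of event and evaluability (9.6); accrual one patient per 2.1 months (9.1); 28-day cycles, up to 26 (4.3).

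**Inputs that are assumptions.** The dates of the two counts and the time from first dose to toxic event are not in the documents. A range is shown for each.

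**Step 1: the plan's own figures, complete status for all children.** Let X be events among the first 9 and Y events among the next 8, both binomial with probability p.

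P(rule met) = P(X≥2) + P(X=0)·P(Y≥4) + P(X=1)·P(Y≥3)

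- p = 0.30: 0.8040 + 0.0404 × 0.1941 + 0.1556 × 0.4482 = 0.8816
- p = 0.10: 0.2252 + 0.3874 × 0.0050 + 0.3874 × 0.0381 = 0.2419

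The 90% is approximately reproduced (88.2%). The figure of about 4% is not: the rule is met 24.2% of the time, roughly six times as often. A search over cut-offs for 9 and 17 patients (first 1 to 7, final up to 9) found no pair that gives 4% and 90% together.

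**Step 2: exposure when the ninth child is first dosed.** Time since first dose for child i is 2.1 × (9 − i) months: 16.8, 14.7, 12.6, 10.5, 8.4, 6.3, 4.2, 2.1 and 0, with mean 8.4. The first count is weakened but not empty.

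**Step 3: detection when the counts are read early.** Each of 17 children, entering 2.1 months apart, has a 30% chance of an eventual toxic event, with onset uniform over the interval shown (400,000 simulated trials per row). Two reductions that take effect on later cycles put the earliest event at about 2 × 28 = 56 days, hence a start at month 2. The last onset row allows for the quicker restart in section 5.1.

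| Assumed onset (months) | First count met, at 9th first dose | Either count met, at 9th and 17th first dose | Either count met, both read 3 months later |
|---|---|---|---|
| 2–24 | 19% | 43% | 57% |
| 2–12 | 48% | 68% | 78% |
| 2–6 | 63% | 77% | 85% |
| 1–3 | 71% | 82% | 88% |
| Complete status | 80% | 88% | 88% |

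If only the first count is early (at the 9th first dose) and the second waits for complete status, detection is 81% to 85% over the first three rows.

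At a 10% incidence with counts at first dose, only the slowest onset comes near 4% (3.8%), and there detection at 30% is 43%.

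**Step 4: a trigger that acts whenever the event occurs.** If the review follows the 2nd event among the first 9 or the 4th among 17 at any date, detection returns to 88.2%. It fires before the 17th first dose (16 × 2.1 = month 33.6) in 76%, 82% and 84% of trials for the first three rows. At a 10% incidence it is eventually met 24.2% of the time.

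Progression, withdrawal and dose delays were not modelled.

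**The case against.** The strongest reply is that 9.6 never ties a count to the 9th or 17th first dose. Evaluability after one dose defines the denominator, not the moment of reading, and a review that follows when the events are observed can be read as an open count. On that reading the rule reaches 88%. This stands: a reader might infer that the 90% is simply not delivered, but the documents do not fix the count dates that this would need. The stage sizes also match the efficacy stages in 9.2 and 9.5. If the toxicity counts waited, as response does, for the first MRI after cycle 3 (7.1), the figures three months later would be the relevant ones.

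A reader might also infer that the first count will usually miss a 30% incidence. That holds only for the slowest onset (19% met). It is met 48% to 71% of the time for the others.

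A third tempting reading is that the plan's own phase I data show late toxicity for this regimen. Section 2.6 reports that dose-limiting toxicity absent in the first 4 weeks at the 3 µg/kg "DL became apparent over time". This trial gives 1 mcg/kg (2.7.1). At 1.0 µg/kg section 2.6 reports one dose-limiting toxicity in 12 patients, without its timing. Late onset at the trial's dose is therefore an inference, and the point does not need it.

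Other safeguards exist. Under 11.2 the DSMB meets regularly and can recommend changes, and it is notified of serious adverse events; 9.8 plans life-table estimates. They lessen the consequence but supply no threshold and do not support the stated 90%.

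**Conclusion.** The concern holds as a defect in how 9.6 is specified. The one-dose denominator and the three-step event do not fit together unless the counts stay open, and the section does not say that they do. Detection at a 30% incidence is 88% with open counts, about 43% to 82% with counts at the 9th and 17th first dose, and about 57% to 88% three months later. The two ranges rest on steady accrual every 2.1 months and on assumed uniform onset; neither onset nor count dates can be taken from the documents.

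Separately, and with no timing assumption, the quoted false-alarm rate is wrong for the rule as written: 24.2% at a 10% incidence with complete status, against about 4% stated. The section should be corrected before the rule is relied on.

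**What to change.** Rewrite 9.6 to state that:

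- the review is triggered as soon as the 2nd toxic event occurs among the first 9 treated patients, or the 4th among the first 17 treated, at any date until the last of them has finished or left treatment. The 17 should be named because 9.1 allows 20 to be enrolled;
- a boundary is not declared unmet while patients in that group are still on drug;
- the 10% and 30% incidences refer to the whole treatment period of up to 26 cycles;
- the rule is met about 88% of the time at 30% and about 24% at 10%.

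If open counts were always intended, the two-stage wording and the one-dose evaluability sentence still need rewording so that they do not read as fixed looks.

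The cost is a paragraph: no extra patients, visits or data. Reviews may fall on unscheduled dates, and the stated false-alarm rate becomes less favourable. The sponsor and the DSMB should decide whether 24% is acceptable for a rule that leads to a review; if not, new boundaries need their own recomputed figures at both incidences.
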